## 7.5.1 Hepatic Toxicity

### 7.5.1.1 Elevations in Transaminases

Treatment management algorithm for patients experiencing hepatic toxicity are as follows:

- Grade 1 elevations - No specific therapy required.
- Grade 2 elevations - For elevations in transaminases 3 to  $5 \times$  ULN, rule out viral and other etiologies, and consider immediate oral steroids such as prednisone 60 mg/day divided twice daily, and hold MGD007 and MGA012.
  - If improvement to  $\leq$  Grade 1 does not occur within 48 hours consider IV steroids such as methylprednisolone at 2 mg/kg/day divided twice daily or oral steroids such as prednisone 60 to 120 mg per day, divided twice daily.
  - Resume MGD007 and MGA012 at the next scheduled dose if no more than 2 doses of the combination were missed.
  - If improvement to  $\leq$  Grade 1 does not occur within 14 days, discontinue MGD007 and MGA012.
- Grade 3 elevations - Hold MGD007 and MGA012.
  - For elevations in transaminases  $> 8 \times$  ULN, permanently discontinue MGD007 and MGA012.
    - Begin immediate IV steroids, and
    - If no response to corticosteroid therapy within 3 to 5 days is observed, consider adding immune suppression therapy with mycophenolate.
    - Monitor liver function tests at least twice weekly (or more frequently as clinically appropriate in the judgment of the Investigator) until transaminases have returned to Grade 1 or baseline.
  - For elevations in transaminases  $> 5$  but  $\leq 8 \times$  ULN:

- Begin immediate IV steroids; suggest methylprednisolone at a dosage of 2 mg/kg/day divided twice daily.
- Consider additional immune suppression as above for patients who do not respond to corticosteroid therapy within 3 to 5 days.
- Monitor liver function tests at least twice weekly (or more frequently as clinically appropriate in the judgment of the Investigator) until transaminases have returned to Grade 1 or baseline.
- If the elevation does not improve to Grade 2 within 7 days and to Grade 1 within 14 days, discontinue MGD007 and MGA012.
- Resume MGD007 and MGA012 administration if following conditions are met:
  - Laboratory elevations downgrade to  $\leq$  Grade 2 within 7 days and improve to  $\leq$  Grade 1 or baseline within 14 days.
  - Steroids have been tapered to  $\leq$  10 mg per day of prednisone or equivalent.
  - On resuming MGD007 and MGA012, AST, ALT, and total and direct bilirubin laboratory test values will be evaluated at least once per week for 3 consecutive weeks.
- Permanently discontinue MGD007 and MGA012 treatment in the case of a second increase of AST or ALT to  $\geq$  Grade 3.
- Grade 4 elevations - Discontinue MGD007 and MGA012 and treat as for Grade 3 elevation. MGD007 and MGA012 should be permanently discontinued.

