### 4.2.3 Hepatic Non-hematologic Dose Limiting Toxicity

Hepatic non-hematologic DLT will be defined as follows:

- Any elevation of one or more transaminases  $> 8 \times$  the institutional upper limit of normal (ULN) irrespective of duration.
- Any Grade 3 elevation of one or more transaminases  $> 5.0 - 8.0 \times$  the ULN that does not resolve to Grade 2 (i.e.,  $> 3.0 - 5.0 \times$  ULN) within 7 days and Grade 1 (i.e.,  $> \text{ULN} - 3.0 \times$  ULN) within 14 days. In addition, steroids must be tapered to  $\leq 10$  mg of prednisone or equivalent per day, by Day 14.
- A Grade 3 elevation of total bilirubin that is  $> 5 \times$  the ULN, irrespective of duration.
- Any Grade 3 elevation of total bilirubin  $> 3.0 - 5.0 \times$  ULN that does not resolve to Grade 2 (i.e.,  $> 1.5 - 3.0 \times$  ULN) within 7 days and Grade 1 (i.e.,  $> \text{ULN} - 1.5 \times$  ULN) within 14 days. In addition, steroids must be tapered to  $\leq 10$  mg of prednisone or equivalent per day, by Day 14.
- Any event meeting the criteria for Hy's law as follows (all 3 features):
  - Aspartate aminotransferase (AST) and/or alanine aminotransferase (ALT)  $> 3 \times$  ULN
  - Concurrent elevation of total bilirubin  $> 2 \times$  ULN without initial evidence of cholestasis
  - No alternative etiology can be identified

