9. For the 15 patients who will have paired tumor biopsies, tumor lesions must be accessible for biopsy with acceptable clinical risk in the judgment of the investigator. Paired tumor biopsies will be mandatory if tumor lesions are accessible for biopsy with acceptable clinical risk in the judgment of the investigator and after discussion with the Sponsor. Fifteen paired biopsies will be required in each cohort at the end of the Cohort Expansion Phase. For each patient, the identified lesion to be biopsied should not have been previously irradiated and should not be the only lesion being utilized as measurable disease target lesion for objective response assessment. The lesion to be biopsied should be of sufficient size to enable acquisition of at least 2 tumor biopsy cores using a biopsy needle.
10. Acceptable laboratory parameters as follows:
  - a. Platelet count  $\geq 100 \times 10^3$ /microliter without transfusion within 4 weeks prior to the initiation of study drug.
  - b. Hemoglobin  $\geq 8.0$  g/dL without transfusion within 1 week prior to the initiation of study drug.
  - c. White blood cell count (WBC)  $\geq 2.0 \times 10^3$ /microliter in the absence of any growth factor support within 4 weeks prior to the initiation of study drug.
  - d. Absolute neutrophil count  $\geq 1.5 \times 10^3$ /microliter in the absence of any growth factor support within 4 weeks prior to the initiation of study drug.
  - e. ALT/AST  $\leq 3.0$  times the ULN, up to 5.0 times the ULN for patients with liver metastases.
  - f. Total bilirubin  $\leq 1.5$  times ULN, except patients with Gilbert's syndrome, who may enroll if the conjugated bilirubin is within normal limits.
  - g. Creatinine  $< 1.5$  mg/dL, or a calculated or measured creatinine clearance  $> 50$  mL/min.
  - h. Negative urine or serum pregnancy test for women of child-bearing potential.

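### The Grade 3 hepatic stop and resume rules in Protocol 7.5.1.1 and 7.5.2 contradict each other for patients eligibly enrolled with ALT/AST or bilirubin already above Grade 1

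*Protocol*

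**What the plan says.** **Entry.** Protocol 5.1 #10e caps ALT/AST at 3.0 × ULN, but "up to 5.0 times the ULN for patients with liver metastases". #10f caps total bilirubin at 1.5 × ULN except for patients with Gilbert's syndrome, "who may enroll if the conjugated bilirubin is within normal limits"; it sets no upper limit on their total bilirubin.

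**Grade bands.** As printed in 4.2.3, Grade 1 ends at 3.0 × ULN for transaminases and 1.5 × ULN for bilirubin. Grade 2 ends at 5.0 × and 3.0 × ULN.

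**Grade 3 management, 7.5.1.1 (above 5 and up to 8 × ULN).** The stop bullet reads: "If the elevation does not improve to Grade 2 within 7 days and to Grade 1 within 14 days, discontinue MGD007 and MGA012". The resume condition requires Grade 2 or lower by Day 7 and accepts, for the second limb, "Grade 1 or baseline within 14 days", with steroids down to 10 mg prednisone or less. The monitoring bullet runs "until transaminases have returned to Grade 1 or baseline". Section 7.5.2 has the same stop, resume and monitoring structure for bilirubin above 3.0 and up to 5 × ULN.

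**Grade 2 management.** Both sections hold the drugs and discontinue them if Grade 1 is not reached within 14 days. Neither mentions baseline.

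**Related rules.** Section 4.2.3 scores as a DLT "Any Grade 3 elevation of one or more transaminases" in the 5.0 to 8.0 × ULN band, and "Any Grade 3 elevation of total bilirubin" in the 3.0 to 5.0 × ULN band, that does not reach Grade 2 by Day 7 and Grade 1 by Day 14, again with no baseline alternative. Section 4.4.1 allows re-treatment when the toxicity is unrelated or is not a DLT, provided it has resolved under Section 7. Section 5.4 lists a drug-related DLT as a reason to stop treatment. The SAP does not address the point.

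**The concern.** The protocol knowingly enrolls patients whose liver tests start above Grade 1, then gives two instructions for the same recovery in that group. Take a patient with liver metastases who enters at ALT 4 × ULN, has a drug-related rise to 5.5 ×, is back at 4 × by Day 7 and still at 4 × on Day 14, with prednisone at 10 mg or less. The stop bullet ends treatment, because 4 × ULN is not Grade 1. The resume bullet restarts it, because 4 × ULN is this patient's baseline.

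At stake is consistent treatment. Two sites reading the same list correctly could discontinue or continue the same recovered patient. In the expansion phase of about 25 patients, that also affects exposure and follow-up on treatment, and so the response data.

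**Working it through.** The plan states no figure on this point, so the check is to apply its rules to cases.

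**1. What the baseline words do.** If baseline is Grade 1 or lower, a return to baseline is already a return to Grade 1 or lower, and the extra words in the resume bullet add nothing. They have effect only when baseline is above Grade 1. Those are exactly the patients the stop bullet removes. The pair therefore cannot be read as a strict stop rule with a compatible resume rule.

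**2. How far below baseline a patient must fall to escape the stop bullet.** Fall needed = 1 − (top of Grade 1 ÷ baseline).

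- ALT/AST, 1 − 3.0/b: entry at 3.5 × ULN, 14%; at 4 ×, 25%; at 5 ×, 40%.
- Bilirubin, 1 − 1.5/b: entry at 1.8 × ULN, 17%; at 2.5 ×, 40%; at 3 ×, 50%.

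**3. Both rules on a grid.** Each case is a Grade 3 rise that is Grade 2 or lower by Day 7 and exactly at baseline by Day 14, with steroids tapered.

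| Entry value (× ULN) | Stop bullet met | Resume laboratory condition met |
|---|---|---|
| ALT/AST 1.0, 2.5, 3.0 | no | yes |
| ALT/AST 3.5, 4.0, 5.0 | **yes** | **yes** |
| Bilirubin 1.0, 1.5 | no | yes |
| Bilirubin 1.8, 2.5, 3.0 | **yes** | **yes** |

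The conflict appears in every case above the Grade 1 band and in none at or below it. With a baseline alternative in the Day 14 limb of the stop bullets, the stop column becomes no in all rows.

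**4. Whether another section settles it.**

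- *Escalation, drug-related event by Cycle 1 Day 42.* The recovery test in 4.2.3 is the same as the stop bullet's, so the patient in the bold rows is a DLT. Section 4.4.1 then gives no route to re-treatment, and 5.4 lists the DLT as a reason to stop. The answer is stop.
- *After Day 42.* The event can no longer be a DLT under 4.2. Section 4.4.1 sends the site to Section 7, where the two bullets disagree. Nothing settles it.
- *Expansion.* Section 4.2 frames DLTs as a guide to escalation decisions, so the tie-break is not clearly available even before Day 42, and is absent afterwards.

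**5. What remains if only the Grade 3 stop bullets are changed.**

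- The example patient sits at 4 × ULN on Day 14, inside the Grade 2 band. The Grade 2 bullet of 7.5.1.1 still says hold, then discontinue if not Grade 1 within 14 days. Section 7.5.2 holds until Grade 1. These bullets would block the resumption just permitted.
- A Gilbert's patient with baseline 3.5 × ULN who rises to 4.5 × and returns to 3.5 × by Day 7 is still above 3.0 × ULN. This patient fails the Day 7 limb of both the stop and the resume bullet unless bilirubin falls 1 − 3.0/3.5 = 14% below baseline.

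**The case against.** The strongest reply is that the protocol as a whole leans toward stopping. Within the escalation DLT window, 4.2.3, 4.4.1 and 5.4 agree with the stop bullet, which leaves the baseline words in the resume bullet as the outlier. Section 7.5 calls its rules general guidelines, and 5.4 allows case-by-case continuation for compelling benefit.

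The first part stands and limits the point: for a drug-related event by Cycle 1 Day 42 in escalation, a careful site has an answer. It does not reach later events or clearly reach expansion. Calling the bullets guidelines does not say which governs, and the 5.4 exception requires compelling benefit and Sponsor consultation rather than recovery to baseline.

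Two stronger readings are tempting, and the documents do not support them.

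- *A reader might infer that the DLT definition in 4.2.3 is itself wrong and distorts escalation.* Its Grade 1 test is clear and internally consistent, and can be a deliberate conservative choice. The baseline-or-Grade-1 wording in 12.2.3 governs how long SAEs are followed, not DLT scoring. The documents do not say how many patients enter above Grade 1 or how often they have such a rise, so any figure for the effect on dose clearance would come only from the inputs chosen.
- *A reader might infer that a patient admitted at Grade 2 must be held from the first dose under the Grade 2 bullets.* Section 12.1.1 defines an adverse event by onset or worsening from baseline, so an unchanged baseline does not trigger them. Those bullets matter here only after a real rise.

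**Conclusion.** The contradiction is real, and it is confined to patients eligibly enrolled with ALT/AST above 3 and up to 5 × ULN, or with Gilbert's bilirubin above 1.5 × ULN, who have a Grade 3 rise, return to baseline by Day 14 and have steroids tapered. Such a patient meets both the discontinue rule and the resume rule. It matters mainly after Cycle 1 Day 42 and in expansion.

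How many patients this touches cannot be estimated from the documents, and it is probably few. Transaminase and bilirubin elevations are absent from the drug-related events listed in more than 10% of the 75 MGD007 patients (2.3.4). None of the four MGA012 patients, of 37, with related events of Grade 3 or higher had a hepatic one (2.5.3). Both are monotherapy data and say little about the combination. No endpoint definition, analysis or sample size changes. The correction is worth making because this is an operative treatment rule and the remedy is a few words.

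**What to change.** 1. In the Grade 3 stop bullets of 7.5.1.1 and 7.5.2, make the Day 14 limb match the resume bullets: "Grade 1 or baseline within 14 days".
2. Add the same baseline alternative to the Grade 2 bullets of both sections, including the hold in 7.5.2 that ends only at Grade 1.
3. In 7.5.2, for Gilbert's patients whose eligible baseline is above 3 × ULN, allow return to baseline at the Day 7 limb. Change the stop and resume bullets together so that no new mismatch arises.
4. Leave the criteria for transaminases above 8 × ULN, bilirubin above 5 × ULN, Hy's law and the steroid taper unchanged.
5. Have the sponsor decide whether 4.2.3 should carry a baseline alternative. That is a safety judgement and not part of the required correction. If Grade 1 only is kept there, state in 7.5 that an event scored as a DLT under 4.2.3 cannot be resumed under the baseline clause.

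The cost is amendment wording, with no new data, visits or patients. Item 1 permits nothing the resume bullets do not already permit. Items 2 and 3 loosen the rules slightly, only for patients whose eligible baseline is above Grade 1, and only as far as that baseline.

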## 7.5.2 Elevations in Total Bilirubin

Management guidelines for patients experiencing elevations in total bilirubin are as follows:

- Grade 1 elevations - No specific therapy required.
- Grade 2 elevations - Hold MGD007 and MGA012 until improvement to  $\leq$  Grade 1.
  - Consider oral steroids.
  - If improvement to  $\leq$  Grade 1 does not occur within 14 days, discontinue MGD007 and MGA012 and begin oral steroids.
- Grade 3 elevations - Hold MGD007 and MGA012
  - For elevations in total bilirubin  $> 5 \times$  ULN, permanently discontinue MGD007 and MGA012 and initiate IV steroids, suggest methylprednisolone at a dosage of 2 mg/kg/day divided twice daily, and,

- If no response to corticosteroid therapy within 3 to 5 days is observed, consider adding immune suppression therapy with mycophenolate.
- Monitor liver function testing at least twice weekly (or more frequently as clinically appropriate in the judgment of the Investigator) until total bilirubin has returned to Grade 1 or baseline.
- For elevations in total bilirubin  $> 3.0$  but  $\leq 5 \times \text{ULN}$ :
  - Begin immediate IV steroids, suggest methylprednisolone at a dosage of 2 mg/kg/day divided twice daily. Consider additional immune suppression as above for patients who do not respond to corticosteroid therapy within 3 to 5 days.
  - Monitor liver function including total bilirubin testing at least twice weekly (or more frequently as clinically appropriate in the judgment of the Investigator) until total bilirubin has returned to Grade 1 or baseline.
  - If the elevation does not improve to Grade 2 within 7 days and to Grade 1 within 14 days, discontinue MGD007 and MGA012.
- Resume MGD007 and MGA012 administration if:
  - Laboratory elevations downgrade to  $\leq$  Grade 2 within 7 days and improve to  $\leq$  Grade 1 or baseline within 14 days.
  - Steroids have been tapered to  $\leq 10$  mg per day of prednisone or equivalent.
  - On resuming MGD007 and MGA012, AST, ALT, and total bilirubin laboratory test values will be evaluated at least once per week for 3 consecutive weeks.
- Permanently discontinue MGD007 and MGA012 in the case of a second increase of total bilirubin to  $\geq$  Grade 3.
- Grade 4 elevations - Discontinue MGD007 and MGA012 and treat as for Grade 3 elevation. MGD007 and MGA012 should be permanently discontinued.

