## 4.2 Dose Limiting Toxicity

For the purpose of guiding dose escalation decisions, dose-limiting toxicities (DLTs) are defined by drug-related AEs that occur up to Cycle 1 Day 42. The severity of AEs will be graded according to the National Cancer Institute Common Terminology Criteria for Adverse Events v 4.03 (NCI CTCAE v 4.03). Dose-limiting toxicities will be defined separately for hematologic, non-hematologic, and hepatic non-hematologic events.

In general, for patients who experience an AE that may meet the criteria for a DLT, subsequent administration of the study drugs should be held pending management and/or resolution of the event and assessment of attribution to the study drug. Criteria for subsequent continuation of therapy are outlined in are outlined below.

Dose limiting toxicities are defined separately for hematologic and non-hematologic events as described below.

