##### **4.4.1 Dose Delays in Escalation and Expansion Cohorts**

Patients who experience toxicity that is potentially dose-limiting should have study drug held pending assessment, management, and resolution of the toxicity. For patients in whom the toxicity is assessed to be unrelated to study drug or for whom the toxicity does not meet the

criteria for DLT, therapy may be re-instituted at the same dose and schedule that was administered prior to the event, presuming the toxicity has resolved as per guidelines outlined in [Section 7](#). Dose interruptions of up to 28 days are allowed. Reinstitution of therapy shall be conducted as follows:

- The procedures at the originally scheduled missed visit should be performed as soon as possible with treatment reinstated as if no delay had occurred, picking up at the day where the interruption occurred, and patients should receive the planned dose and have assessments performed as outlined in the Time and Events Schedule ([Appendix 1](#)).

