## 5.4 Rules for Study Treatment Discontinuation

Patients who tolerate treatment may continue to receive treatment with the study drug(s) as specified in the protocol until any one of the following conditions are met:

- Patient meets any criteria for immune-related disease progression (irPD)
- Withdrawal of patient due to an AE or SAE
- Withdrawal of patient consent
- Completion of protocol-defined therapy
- Investigator discretion
- Pregnancy
- Occurrence of drug-related DLT
- Dose delay > 28 days due to drug-related AE
- Repeated administration of prohibited concomitant medications
- The Sponsor, Investigator, or Regulatory Agency terminates the study
- Death

For individual patients who meet these criteria, but who are otherwise considered to be experiencing compelling clinical benefit in the judgment of the Investigator, consideration may be given to continue treatment with the MGD007 and MGA012 combination, for up to maximum of total of 12 cycles, on a case-by-case basis, in consultation with the Sponsor.

For patients who experience drug-related DLTs that occurs prior to the initiation of MGA012, or for selected immune-related adverse events clearly related to the mechanism of action of MGA012, continued treatment of patients with either MGA012 or MGD007 monotherapy, respectively, may be considered selectively on a case-by-case basis, in consultation with the Sponsor.

If the Investigator decides that the patient should be withdrawn from the study or from dosing for any reason other than disease progression, the site must enter the information in the eCRFs within 24 hours ([Section 12.2.2](#)).

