## 12.2.2 Immediately Reportable Events

Immediately Reportable Events (IREs) are events that must be reported immediately to MacroGenics within 24 hours of the study site’s awareness of the event.

- SAEs
- Pregnancy in a study patient or partner of a study patient. [Note: If the female partner of a male patient becomes pregnant, the partner must be requested to complete a Pregnant Partner Consent Form so that pregnant partner, fetal and/or newborn information can be collected.] Upon confirmation of serum pregnancy testing, the patient will be followed for the outcome of pregnancy. All live newborns will be followed 6 months after the birth, and all necessary information will be collected to assess the effects of study drug on the newborn. If necessary, the follow-up period will be extended for the newborn.
- The following AESIs ([Section 12.2.4](#)):
  - $\geq$  Grade 3 IRRs or CRS
  - Grade 2 or greater immune-related AEs of the following: events of colitis, pneumonitis, hepatitis, Stevens-Johnson syndrome (SJS), and toxic epidermal necrolysis (TEN), myocarditis, nephritis, hypophysitis, and hypo/hyper-thyroidism which are considered immune-mediated events
  - Abnormal liver enzymes that meet the criteria for potential Hy’s law, which is defined as AST and/or ALT that is greater than  $3 \times$  ULN and total bilirubin that is greater than  $2 \times$  ULN and without any alternate etiology
  - Grade 2 or greater diarrhea associated with visible blood in the stool or melena
  - Any Grade 3 or greater diarrhea irrespective of evidence of GI bleeding
- Administration of a dose significantly greater (specifically, + 20% or higher) than the planned dose, and results in an event of clinical consequence.

- AEs leading to permanent discontinuation of study drug in an individual patient.
- Withdrawal of the patient from study drug administration for any reason other than disease progression.

In those cases, in which the IRE is considered related to study drug, the study drug may be discontinued, and the patient will continue participation in the study for observational safety and analysis (except for cases where the patient is withdrawn from the study by the Investigator or withdrew the consent). At any time after completion of the study, if an Investigator becomes aware of a serious adverse event that s/he suspects is related to study drug, the Investigator should report the event to MacroGenics Product Safety.

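### The liver rules in 7.5.1.1 and 7.5.2 act on each test alone, so both drugs may be resumed after a Hy's-law event that 4.2.3 makes a DLT and 5.4 lists as a reason to stop

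*Protocol*

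**What the plan says.** Section 4.2.3 lists five hepatic DLTs. The last is "Any event meeting the criteria for Hy's law as follows (all 3 features"): AST and/or ALT above 3x ULN; a concurrent total bilirubin above 2x "ULN without initial evidence of cholestasis"; and no other cause found. Section 5.4 gives "Occurrence of drug-related DLT" among the reasons to end study treatment, and lets the investigator and sponsor continue treatment case by case for compelling benefit. Section 4.4.1 covers toxicity that is unrelated to study drug or does not meet DLT criteria. For those cases "therapy may be re-instituted at the same dose and schedule that was administered prior to the event", provided it has resolved as Section 7 describes.

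Section 7.5 handles the two tests separately. For Grade 2 transaminases, 7.5.1.1 holds both drugs and then says "Resume MGD007 and MGA012 at the next scheduled dose if no more than 2 doses of the combination were missed", with discontinuation if Grade 1 is not reached within 14 days. For bilirubin, 7.5.2 reads "Grade 2 elevations - Hold MGD007 and MGA012 until improvement to" Grade 1 or less, again with a 14-day limit. Both sections also give a resume route for part of Grade 3.

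Section 12.2.2 makes the event immediately reportable ("Abnormal liver enzymes that meet the criteria for potential Hy’s law, which is defined as AST and/or ALT that is greater than" 3x ULN, with bilirubin above 2x ULN), and treats stopping the drug as optional when such an event is related. Section 4.2 says that DLTs "are defined by drug-related AEs that occur up to Cycle 1 Day 42", for the purpose of escalation decisions.

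**The concern.** One event has different consequences depending on the section consulted: a reason to stop in 5.4, not open to restart under 4.4.1 if drug-related, an optional stop in 12.2.2, and a conditional hold-and-resume in 7.5. Section 7.5 is where a site looks when a liver test comes back abnormal, and nothing there signals that the combination of tests changes the answer.

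The first stake is safety. The resume rules, followed as written, could restart both drugs after an event that the protocol itself treats as dose-limiting.

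The second is consistency of the data. Sites could handle the same event differently. That would affect the counts of AEs leading to discontinuation or interruption (SAP 6.7.1) and dose intensity (SAP 6.4). The DLT count used for escalation is not affected, because 4.2.3 classifies the event whatever is done with the drugs afterwards.

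**Working it through.** The plan has no figure to reproduce here; this is a check of the rules against one another.

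**Inputs.** From 4.2.3: transaminases are Grade 2 at >3.0–5.0x ULN, with a Grade 3 sub-band at >5.0–8.0x; bilirubin is Grade 2 at >1.5–3.0x, with a Grade 3 sub-band at >3.0–5.0x; the Hy's-law thresholds are AST/ALT >3x and bilirubin >2x. From 7.5.1.1 and 7.5.2: permanent discontinuation at AST/ALT >8x or bilirubin >5x.

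**Step 1: what 7.5 alone does with a Hy's-law event.** I assume that with both tests raised, the conditions of both sections must be met.

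| AST/ALT (x ULN) | Bilirubin >2–3 | Bilirubin >3–5 | Bilirubin >5 |
|---|---|---|---|
| >3–5 | may resume (Grade 2 on both) | may resume | permanent stop |
| >5–8 | may resume | may resume | permanent stop |
| >8 | permanent stop | permanent stop | permanent stop |

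There are 3 × 3 = 9 combinations: 2 × 2 = 4 allow resumption and 9 − 4 = 5 do not. Only one of the nine is Grade 2 on both tests; ALT 4x with bilirubin 2.5x ULN is an example.

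**Step 2: conditions on resumption.** The Grade 2 transaminase route needs no more than two missed combination doses, and ends in discontinuation if Grade 1 is not reached within 14 days. Grade 2 bilirubin has the same 14-day limit. The Grade 3 routes need Grade 2 or less within 7 days, Grade 1 or less (or baseline) within 14 days, and steroids tapered to 10 mg per day or less of prednisone equivalent. Liver tests are then repeated weekly for three weeks, and a second Grade 3 rise is a permanent stop.

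**Step 3: match the DLT bullets with 7.5.** AST/ALT >8x, AST/ALT >5–8x not resolving in 7 and 14 days, bilirubin >5x, and bilirubin >3–5x not resolving in 7 and 14 days each have a matching discontinuation in 7.5. Hy's law is the only one of the five without a counterpart.

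**Step 4: after Day 42.** If the day limit in 4.2 is part of the definition, a Hy's-law event on Day 43 is not a DLT. The 5.4 DLT criterion then does not reach it, and 4.4.1 passes it to Section 7. If the limit only serves escalation decisions, the criteria still work as severity criteria. Two features favour that second reading: 4.4.1 is headed as covering expansion as well as escalation cohorts and applies the DLT criteria in both, and 5.4 states no day limit. The text does not settle it.

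**Step 5: the definitions differ.** Section 12.2.2 leaves out the cholestasis feature in 4.2.3, so an event can be reportable as Hy's law without being a DLT.

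**The case against.** The strongest reply is that the protocol already ranks these passages. Section 4.4.1 opens restart only when the toxicity is unrelated or does not meet DLT criteria, and turns to Section 7 only after that. Section 7.5 calls itself general guidance, while 5.4 is headed as rules. Section 4.2 has drug held while attribution is assessed. The event goes to the sponsor within 24 hours, and 5.4 also allows stopping for an AE or at the investigator's discretion. The 7.5 resume routes demand real recovery, and the 7.5.2 hold binds even when the transaminase rule is satisfied.

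Most of this stands, and it limits the point. Inside the DLT window the problem is a conflict between passages, not a missing stop rule. A reader might infer that sites would re-expose patients; the documents do not support that, given the 4.4.1 condition, the reporting duty and the recovery limits. A reader might also infer that every Hy's-law event is handled as two Grade 2 findings, but that fits one of the nine combinations.

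The reply does not remove the gap. Sections 7.5.1.1 and 7.5.2 do not refer back to 4.2.3, 4.4.1 or 5.4. The note closing 7.5.7, which covers events in 7.2 to 7.5, mentions DLTs only to allow one drug to continue alone in selected cases. The 4.4.1 condition also depends on the event being a DLT, which is the open question after Day 42.

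**Conclusion.** The point holds as an inconsistency that should be fixed. For a drug-related event meeting all three 4.2.3 features, with AST/ALT above 3x and up to 8x ULN and bilirubin above 2x and up to 5x ULN, Section 7.5 allows conditional resumption of both drugs, while 4.2.3 and 5.4 make the event a reason to stop and 4.4.1 does not open restart. That is four of nine band combinations.

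After Day 42, including later treatment in the expansion phase, the finding is ambiguity. A reader might conclude that the 5.4 stop definitely lapses on Day 43; the documents do not go that far. Nor is the 5.4 stop absolute inside the window, since it carries its own exceptions.

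The conclusion rests on the grade bands in 4.2.3 and on applying both single-test rules together. The documents give no rate for such events, so no expected number of patients can be stated. The share of maximum treatment time falling after Day 42 would not stand in for one.

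**What to change.** Reconcile 4.2, 4.2.3, 4.4.1, 5.4, 7.5.1.1, 7.5.2, the note closing 7.5.7, and 12.2.2. Specifically:

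- At the head of 7.5.1, state that the single-test resume rules there and in 7.5.2 do not govern an event meeting the 4.2.3 Hy's-law definition, and cross-refer to the one action the sponsor chooses.
- State whether that action applies after Cycle 1 Day 42 and in the Cohort Expansion Phase.
- Use one Hy's-law definition in 4.2.3 and 12.2.2, or say why they differ.

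Which clinical action applies is the sponsor's decision. The cost is protocol wording only: the chemistry panel in Appendix 2 already contains AST, ALT and bilirubin, Appendix 1 already schedules it at dosing visits, and the event is already reportable within 24 hours.
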